Title: TMS Related Biomarker Assessments

NCT number: NCT05660018

Document date: 01/18/2023

PI: [name], PHD

Study protocol

Background

Electrical neural oscillations of the brain can be measured at many levels, ranging from single cell to local field potentials in animals, to large-scale synchronized activities in the human scalp. New evidence suggests that there may be common underlying abnormalities in oscillatory activities that are associated with schizophrenia-related cognitive and functional impairments. There is currently no treatment for these electrical oscillation dysfunctions. Transcranial magnetic stimulation (TMS) provides a non-invasive means for altering brain electrical neural activity. TMS has been approved by FDA for the treatment of depression and many other mental disorders. It has been used in a wide range of clinical research, especially in neurology and psychiatry. The investigators aim to develop TMS paradigms that will modulate brain responses during basic sensory to more complex cognitive performance and determine the parameters in anatomic locations and TMS modalities that may effectively and safely modulate neural activities. If the current experiments successfully identified TMS methods/paradigms that improve neural oscillation and cognitive performances in schizophrenia patients, in the future (not part of the current protocol), the investigators can then develop specific TMS treatment that may correct abnormal brain function and improve cognition and clinical symptoms of schizophrenia.

The purpose of this research is to better understand how brain electric activities are changed during TMS. We will test the hypothesis that repetitive TMS pulses, such as theta-burst stimulations, and conventional low- and high-frequency stimulations (Huang et al 2005 *Neuron*; Williams et al 2018 *Brain*), will facilitate EEG neural oscillatory activities, cognitive behaviors, TMS-related responses, and fMRI brain circuitry measure improvement in schizophrenia patients.

Study Procedures

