Brain wave recording: A paste is used to attach the electrodes during brain wave testing, which may irritate the skin on the scalp or face. Irritation is mild and usually resolves quickly. We may ask you to not use hair products on the day of testing (or it has to be washed out prior to testing, which may be inconvenient). The electrode cap you wear can be tight and not comfortable, but it can be adjusted. The tasks can be quite long, boring, or even annoying. Some of the sounds can be loud and uncomfortable. We will give frequent breaks in-between. You can always ask for a break or re-schedule for another time to complete the study.

All safety measures to lessen any side effects will be taken. If you feel that you want to leave the study, you are free to do so at any time. If we feel that you should not continue, we will end the study. We may do this even if you do not want to end the study.

Because TMS is relatively new, its long-term effects are still unknown. We will monitor you at every visit. There may be risks in this study which are not yet known. You will be told of any new findings during the course of this study that may affect your participation. If you feel that you have an illness or symptoms related to your being in the study you should call us.

Statistical Analysis Plan

Demographics were compared using ANOVA or χ^2 tests. We will examine the differences in performances of biomarkers in active TMS compared to sham TMS. We will explore effects of age, sex, baseline medication, cognition, smoking status, and functional measures on biomarkers, and significant findings will be included as covariates. Exploratory analyses were conducted comparing active TMS vs. sham at different time points using independent-sample t-test and comparing baseline vs. post-TMS measurements using paired-sample t-tests at $p < 0.05$. Effect sizes were calculated for nominally significant measures using Cohen's d. All tests were two-tailed.

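### The Background declares a hypothesis test over four domains, but the Statistical Analysis Plan gives no primary biomarker, time point, model, multiplicity control or success rule, and the tests it does specify do not fit the active-versus-sham question

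*Combined protocol and SAP*

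**What the plan says.** The Background announces a confirmatory aim: "We will test the hypothesis that repetitive TMS pulses" of several kinds "will facilitate EEG neural oscillatory activities, cognitive behaviors, TMS-related responses, and fMRI brain circuitry measure improvement in schizophrenia patients". That is four outcome domains and a stated direction.

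Under Study Procedures (EEG/ERP recording), each participant has one active and one sham session on different days, with measurements before and after each. About 30 people take part.

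The Statistical Analysis Plan is one paragraph. Its sentence on the main comparison is "We will examine the differences in performances of biomarkers in active TMS compared to sham TMS". It then specifies two kinds of biomarker test:

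- "Exploratory analyses were conducted comparing active TMS vs. sham at different time points using independent-sample t-test"
- "comparing baseline vs. post-TMS measurements using paired-sample t-tests", at a threshold of 0.05

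It adds "All tests were two-tailed". Cohen's d is to be calculated only for measures that reach nominal significance. Covariates enter if an exploratory analysis finds them significant.

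**The concern.** A declared hypothesis needs a test whose result settles it. Here the main comparison is named only in general terms (active against sham), and no biomarker, assessment time or model is attached to it. No multiplicity control is given across the four domains or across measures within a domain, and no rule says what result would support the hypothesis.

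The tests that are spelled out do not fill the gap. Each participant is measured before and after both active and sham stimulation, so the effect of interest is the active-minus-sham difference in post-minus-pre change. The independent-sample test ignores that the same people supply both sessions. The pre-post test within a session has no sham control, so practice, fatigue or time effects pass straight into it.

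At stake is how the result can be read. The Background says that successful paradigms would lead to later treatment development. As written, a reader could not tell a planned confirmation from the most favourable of many nominal results.

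**Working it through.** The plan gives no error rate, power or effect size, so there is no figure of its own to reproduce. The check asks how the specified tests behave when TMS has no effect.

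**Inputs from the documents.** 30 participants; two sessions each; measurements before and after; independent-sample t-tests of active against sham; paired t-tests of before against after; two-sided 0.05 per test; four domains.

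**Assumptions.** Within-person correlation r = 0.6 between any two occasions (0.3 as an alternative); correlation between biomarkers 0 to 0.3; 4, 10 or 20 biomarkers. Four is one per domain. Ten and 20 are illustrations, because the documents give no count; Study Procedures lists several fMRI tasks and several EEG paradigms.

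**Step 1: size of the independent-sample test on same-person data.** With 58 degrees of freedom the critical value is 2.00. The true variance of the mean difference is (1 − r) times what the test assumes, so the effective cut-off is 2.00/√(1 − r).

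- r = 0.3: 2.00/√0.7 = 2.39, a true size of about 2%.
- r = 0.6: 2.00/√0.4 = 3.16, a true size of about 0.3%.

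The test is far too conservative, so it would also miss real effects.

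**Step 2: where the false positives come from.** The paired tests hold their 5% each. For uncorrelated biomarkers, with a before-after test in each session, the chance of at least one hit is 1 − 0.95^(2m):

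- m = 4: 1 − 0.95^8 = 33.7%
- m = 10: 1 − 0.95^20 = 64.2%
- m = 20: 1 − 0.95^40 = 87.1%

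These nearly equal the simulated totals in Step 3, so at r = 0.6 almost all the risk lies in the tests without a sham control.

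**Step 3: simulation of all four tests per biomarker** (active vs sham before; active vs sham after; before vs after in active; before vs after in sham), n = 30, r = 0.6:

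| Biomarkers | Any nominal p < 0.05 | Favourable only, on active vs sham after or active before vs after |
|---|---|---|
| 4 | 31-35% | 9-10% |
| 10 | 59-65% | 18-23% |
| 20 | 79-88% | 28-41% |

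The last column agrees with 1 − 0.975^m for the active pre-post test alone with uncorrelated biomarkers: 9.6%, 22.4% and 39.7%. At r = 0.3 the any-hit figures are 38-40%, 64-73% and 85-92%.

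**Step 4: comparator.** One pre-specified active-minus-sham change contrast has a 5% two-sided error, or 2.5% in the favourable direction.

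**Step 5: what the missing sham control can do.** Sessions last 4 to 5 hours. Suppose practice or fatigue shifts a measure by 0.2 SD equally in both sessions (assumed). At r = 0.6 the SD of the change is √(2 × 0.4) = 0.894. The noncentrality is (0.2/0.894) × √30 = 1.22, and the active pre-post test is significant about 22% of the time. Over four independent measures that is 1 − 0.78^4 = 63% for at least one. The active-minus-sham change contrast stays at 5%, because the shift cancels.

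**The case against.** The best defence is that the t-tests at 0.05 are expressly labelled exploratory and their results only nominally significant, while the main active-versus-sham comparison stands in a separate sentence with no test or p-value. On that reading the main model is unspecified; it is not shown to leave out the difference in change. This is fair as to wording. But if the t-tests are exploratory, the hypothesis in the Background has no specified test at all.

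A reader might infer that any nominal result would count as support, and that a false positive is therefore likely. The documents do not support that. They nowhere say that one exploratory result confirms the hypothesis. The hypothesis is directional, so a difference before stimulation, a change in the sham session or a worsening could not support it. Once these are set aside, the rate is below 50% in every row of the table. It passes 50% only under more extreme assumptions: about 60% with 20 uncorrelated biomarkers and no within-person correlation. Even the any-hit rate is only about one in three at four biomarkers, the one count tied to the text.

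It can also be said that a study of about 30 people may properly be exploratory throughout, and that softening the Background's language would remove the mismatch. It would, but the independent-sample test would still be the wrong one for this design and the pre-post tests would still lack a control.

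**Conclusion.** The point holds as a missing primary analysis and decision rule, together with specified tests that do not fit the design. It does not hold as a claim that false support is probable.

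At r = 0.6, false favourable results run at roughly 4 times the 2.5% benchmark with four biomarkers (9-10%) and 11 to 16 times with 20 (28-41%). The independent-sample test runs at about 0.3% instead of 5%. These sizes depend on the assumed correlations and on the number of biomarkers, which the plan does not state. The absence of a primary measure, time point, model, multiplicity control and success rule depends on no assumption.

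**What to change.** State in the Statistical Analysis Plan that the hypothesis is tested by the within-participant active-minus-sham difference in post-minus-pre change, two-sided at 0.05, on one primary biomarker at one post-TMS time point. The investigators should choose both before unblinding; the Background does not rank the domains, so the choice is theirs. If they want a claim in each domain, name one biomarker per domain and test each at 0.05/4 = 0.0125. Say that the hypothesis is called supported only on that basis.

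Report all other comparisons as exploratory, with estimates and 95% confidence intervals for every measure, not only those that reach nominal significance, and with false-discovery-rate control within each domain. Replace the independent-sample test with a paired one.

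No procedure or visit changes. The cost is that fewer results can be called significant, and that the investigators must commit to a primary measure, which is a scientific decision as well as a drafting one.

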EEG/ERP recording: subjects will be asked to wear a cap containing electrodes. Electrode paste will be used to facilitate the connection. Subjects may listen to sound stimulations by wearing a pair of headphones, hearing tubes, or through loudspeakers. Tests may include resting EEG, passive and active cognitive tasks. In resting EEG, subjects are asked to relax during brain wave recording. In brain wave recording during passive task: subjects may be asked to relax while sounds at different frequencies and durations are presented to elicit evoked potentials, which can be accompanied by visual presentations. No performance is required except to be alert. In brain wave recording for attention and memory tasks: subjects are asked to pay attention to auditory and visual stimuli while holding a response pad. They are trained and then perform the tasks by responding, remembering, or recalling certain items and ignoring the other items. These tasks are computerized auditory and visual stimuli and data are digitally recorded. Each test may last a few minutes to about half an hour; they are repetitive but with breaks between tasks to reduce subject fatigue. All recordings are stored in secure servers/computers using only a code.

TMS will be given in 2 sessions in 2 different days that are separated by one or more days. In one session you will receive active TMS. In another session you will receive sham TMS. The active or the sham TMS are delivered to one, two or three locations on your scalp. The TMS is given in about 4 minutes for each location. Therefore, in the active TMS day, you will receive 3 TMS administrations in three locations, one after another, for a total of about 12 minutes. In the sham TMS session, you may feel or hear similar TMS, but no actual TMS is stimulating your brain. TMS-evoked responses, brain waves, and MRI will be measured before and after each session to determine the TMS effects. It will take about 4 to 5 hours. It includes about 2 hours before and 2 hours after the TMS where we will perform clinical assessments, TMS-evoked responses, brain wave, and MRI assessments as described above. It also includes time to wear the electrode cap and remove the electrode cap and cleaning the hair after the experiment. About 30 participants will participate in this study.

Research Related Risks

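### Covariates are chosen by significance and cognition is not limited to pre-TMS scores, so the plan permits adjustment for a score that TMS is expected to change

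*Combined protocol and SAP*

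**What the plan says.** The Statistical Analysis Plan is one paragraph. It names the active-sham comparison of biomarkers and then the factors to be examined: "We will explore effects of age, sex, baseline medication, cognition, smoking status, and functional measures on biomarkers". Factors found significant become covariates: "cognition, smoking status, and functional measures on biomarkers, and significant findings will be included as covariates". It does not give a significance threshold for this step, a model in which the covariates would enter, or a primary biomarker. The t-tests it names take no covariates. The word *baseline* stands before medication only.

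Three other places bear on this:

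- The hypothesis in the Background is that repetitive TMS "will facilitate EEG neural oscillatory activities, cognitive behaviors, TMS-related responses, and fMRI brain circuitry measure improvement in schizophrenia patients". Cognition is therefore a hypothesised outcome.
- Study Procedures sets out a within-person design: "TMS will be given in 2 sessions in 2 different days that are separated by one or more days", one active and one sham. It also says "TMS-evoked responses, brain waves, and MRI will be measured before and after each session to determine the TMS effects", and it places clinical assessments in the periods both before and after TMS.
- The EEG/ERP section states "Tests may include resting EEG, passive and active cognitive tasks" and describes attention and memory tasks. Post-TMS cognitive performance may therefore be on file.

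The planned size is given as: "About 30 participants will participate in this study".

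**The concern.** A covariate in a treatment comparison should be fixed in advance and should be something the treatment cannot have changed. The SAP's rule secures neither. The covariates depend on what is significant in the same roughly 30 people who supply the active-sham test, and one candidate, cognition, is also expected to respond to TMS.

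If a post-TMS cognition score passes the screen, the adjusted estimate answers a different question: how far active and sham differ at equal post-session cognition. Any part of the biomarker change that travels with the cognitive change is taken out. A weak adjusted result could then reflect over-adjustment, and a reader of the results could not tell.

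There is also a missed opportunity. In a two-session design the covariate most likely to sharpen the contrast is the same biomarker measured just before stimulation in that session. It is not on the list.

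**Working it through.** The documents give no effect size, SD or power calculation, so there is no planned figure to reproduce. The inputs are 30 participants with one active and one sham session each (Study Procedures) and two-sided tests (SAP). The screening level of 0.05 is an assumption, because the SAP states 0.05 only for its exploratory t-tests. All effect sizes, slopes and correlations below are assumptions.

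**1. Covariates constant within a person.** With complete pairs, the contrast is the mean of (active − sham) within people. Age and sex, and medication and smoking status if taken at baseline, have the same value in both sessions, so their difference is 0. In 4,000 simulated crossovers with six such covariates screened at 0.05, the estimate was 0.498 with and without adjustment (largest difference 6e-16). They neither bias nor improve the paired contrast. The same holds for a pre-TMS person-level cognition score.

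**2. Post-TMS cognition.** Let the true effect be 0.50 SD (SD of the biomarker apart from its cognition-linked part), the TMS shift in cognition *t*, and the biomarker's slope on cognition *g*. If cognition is always retained, the adjusted estimate is 0.50 − *g* × *t*. For example, 0.50 − 0.3 × 0.3 = 0.41 and 0.50 − 0.5 × 0.5 = 0.25, losses of 18% and 50%.

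The SAP describes a screen, so cognition would not always be retained. A simulation (4,000 runs per setting, within-person correlation 0.5) kept cognition only if the within-person differences in biomarker and cognition correlated at p < 0.05:

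| *g* | *t* | Always retained | Share of runs selecting cognition | Mean estimate after screen | Power, unadjusted → screened |
|---|---|---|---|---|---|
| 0.3 | 0.3 | 0.41 | 0.348 | 0.448 | 0.712 → 0.627 |
| 0.3 | 0.5 | 0.35 | 0.347 | 0.414 | 0.714 → 0.553 |
| 0.5 | 0.3 | 0.35 | 0.710 | 0.380 | 0.661 → 0.485 |
| 0.5 | 0.5 | 0.25 | 0.719 | 0.290 | 0.661 → 0.314 |
| 0.7 | 0.3 | 0.29 | 0.933 | 0.302 | 0.602 → 0.326 |
| 0.7 | 0.5 | 0.15 | 0.929 | 0.160 | 0.576 → 0.128 |

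For slopes of 0.3 to 0.5, the loss after the screen runs from (0.50 − 0.448)/0.50 = 10% to (0.50 − 0.290)/0.50 = 42%. With *t* = 0 the mean estimate stayed at 0.50 for every slope, so absorption requires that TMS shifts cognition. If shift and slope had opposite signs, the error would run the other way.

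**3. The session's own pre-TMS value.** Let *w* be the pre-post correlation within a session and *b* the correlation between sessions. Regressing the post-TMS difference (active − sham) on the pre-TMS difference, the two differences correlate at (*w* − *b*)/(1 − *b*). With *b* = 0.5:

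- *w* = 0.7 gives 0.2/0.5 = 0.4, and √(1 − 0.16) = 0.917.
- *w* = 0.8 gives 0.3/0.5 = 0.6, and √(1 − 0.36) = 0.800.
- Estimating the extra slope from 30 pairs multiplies the standard error by about √(1 + 1/27) = 1.018.

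The net factors are 0.917 × 1.018 = 0.933 and 0.800 × 1.018 = 0.815. Simulation gave reductions in the standard error of about 7% and 18%, with no bias. If *w* is no larger than *b* = 0.5, the cost is about 2%.

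**The case against.** The best reply is that the SAP's list reads as a set of participant characteristics, that *baseline* can be carried across it, and that nowhere do the documents say a post-TMS score will be a covariate. This is fair. On that reading nothing is absorbed. But the text does not settle it, and the hypothesis and the post-session assessments make the other reading available. It is also fair that the SAP presents this step as exploration and that the loss figures rest wholly on assumed inputs.

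Four stronger readings are tempting and are not supported:

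- *Screening noise covariates damages the treatment test.* Six null candidates at 0.05 give a 1 − 0.95^6 = 26.5% chance of keeping at least one, and more if repeated rows are treated as independent. But person-constant covariates leave the paired contrast unchanged. In a 30 versus 30 null comparison with covariates selected this way, type I error was 4.8%. The SAP also does not describe a stacked-row screen. These percentages are not evidence of harm.
- *Each biomarker will have its own model.* The SAP does not say whether selection is made per biomarker or once for all.
- *Functional scores will be affected in the same way.* The hypothesis does not list function as an outcome, and no functional measure is named among the post-session assessments.
- *The plan will adjust for post-TMS cognition.* It permits this; it does not state it.

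**Conclusion.** The point holds in limited form. The SAP's rule chooses covariates by significance in the trial data and leaves the timing of cognition open, although cognition is a hypothesised outcome.

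Bias arises only if three things are true together: cognition is scored after TMS, it passes the screen, and TMS shifts it. In that case, under the assumptions shown with slopes of 0.3 to 0.5, a 0.50 SD effect falls to 0.41 to 0.25 SD if cognition is always retained, and to 0.45 to 0.29 SD with the screen. If cognition is a pre-TMS person-level value, the within-person contrast is unchanged and what remains is freedom to choose the model after seeing the data. Separately, the plan leaves out the one covariate that could improve precision. The change should be made; it is cheap and removes the ambiguity.

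**What to change.** Replace the covariate sentence with a rule along these lines:

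- Every biomarker is analysed with the same within-participant active-sham model, for example the post-TMS difference between a person's two sessions regressed on the pre-TMS difference, so that each session's own pre-TMS value of that biomarker is the covariate.
- Session number is added only if session order varies between participants. Study Procedures does not say whether it does. If the order were the same for everyone, session and condition could not be separated and the term could not be fitted.
- No covariate is selected by p-value, and no post-TMS score is used as a covariate.
- Age, sex, medication, smoking, and cognition and function measured before the first session are kept as exploratory moderators, each as a factor-by-condition interaction.

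The cost is SAP wording, one degree of freedom (about 2% on the standard error if the pre-TMS value proves uninformative) and the loss of ad hoc covariates. No new measurement is needed for the adjustment, since pre-TMS biomarker values are already collected in each session.

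### Every participant has both active and sham sessions, but the SAP's only named active-vs-sham test treats them as separate groups, and no paired, baseline-adjusted contrast is specified

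*Combined protocol and SAP*

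**What the plan says.** The session description, under EEG/ERP recording in Study Procedures, sets out a two-period within-participant design:

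- "In one session you will receive active TMS. In another session you will receive sham TMS".
- "TMS will be given in 2 sessions in 2 different days that are separated by one or more days". No order of sessions is given.
- "TMS-evoked responses, brain waves, and MRI will be measured before and after each session to determine the TMS effects".
- "About 30 participants will participate in this study".

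Each biomarker therefore has four linked values per person: before and after active, and before and after sham.

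The Statistical Analysis Plan makes three statements about biomarker comparisons:

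- A general aim: "We will examine the differences in performances of biomarkers in active TMS compared to sham TMS". No scale, test or model is given.
- An exploratory between-condition test: "comparing active TMS vs. sham at different time points using independent-sample t-test".
- An exploratory within-session test: "comparing baseline vs. post-TMS measurements using paired-sample t-tests". Baseline is not defined.

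Covariates are to be added if they prove significant. The list does not include the session's own pre-TMS biomarker value. ANOVA is named only for demographics.

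**The concern.** The independent-sample t-test does not fit a design in which the same people supply both sets of values. It computes its standard error as if the two means were uncorrelated. When a person's two sessions are positively correlated, that standard error is too large, the test rejects too rarely, and the main benefit of giving everyone both conditions is lost. With about 30 people, a real effect can then be missed.

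The paired pre-post test has the opposite weakness. It uses the pairing but has no sham comparison, so any change over a visit of 4 to 5 hours counts as change after TMS. The protocol itself says of the tasks that "they are repetitive but with breaks between tasks to reduce subject fatigue", so practice and fatigue are foreseeable. Drift common to both sessions cancels in an active-vs-sham contrast but not in a pre-post test. A significant pre-post result read alone could be taken for a TMS effect that is not there.

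Neither test combines the pairing, the sham control and the pre-TMS value, and the general sentence leaves the method open.

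**Working it through.** **No figure to reproduce.** The sample size comes without power, effect size, SD or correlation.

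**Inputs.** From the documents: n = 30 (about 30), two conditions per person, pre and post in each, two-sided 5%. Assumed: variances for person 0.5, session 0.2 and residual 0.3 (total SD 1). This gives a correlation of 0.5 between sessions and 0.7 within a session. Seven other splits give the ranges: 0.6/0/0.4, 0.7/0.1/0.2, 0.4/0.3/0.3, 0.3/0.3/0.4, 0.6/0.1/0.3, 0.5/0.3/0.2 and 0.3/0.2/0.5. All 30 pairs are taken as complete.

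**Standard error of the active-minus-sham post-TMS difference**

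1. Independent, as that test computes it: √(2 × 1/30) = 0.258.
2. Paired, post-TMS only (person variance cancels): √(2 × (0.2 + 0.3)/30) = 0.183. The variance is halved.
3. Paired and adjusted for the pre-TMS difference. The pre and post differences correlate at 0.2/(0.2 + 0.3) = 0.4. With the slope estimated: 0.183 × √((1 − 0.16)(1 + 1/27)) = 0.170.
4. As 3, with an order term and orders split 15/15: 0.183 × √((1 − 0.16)(1 + 1/26)) = 0.171.

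The variance gain from adjustment is 1 − 0.84 × (1 + 1/27) = 12.9%, or 12.8% with the order term. Over the eight splits it runs from a 4% loss (no session variance) to a 34% gain.

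**Why the independent test is conservative.** It rejects when the difference exceeds about 2.00 × 0.258 = 0.517. The true standard error is 0.183, so under no effect this is 0.517/0.183 = 2.83 standard errors, a two-sided probability of about 0.5%. Simulation, which also lets the variance be estimated, gives 0.7%.

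**Power (40,000 simulated trials per setting)**

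| Analysis | 0.5 SD | 0.3 SD | 0.5 SD, range over splits |
|---|---|---|---|
| Independent t-test | 47% | 13% | 46–48% |
| Paired, post-TMS only | 75% | 36% | 61–93% |
| Paired, adjusted | 81% | 40% | – |
| Paired, adjusted, order term | 81% | 40% | 63–94% |

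**Pre-post test with no TMS effect.** Its standard error is √(2 × 0.3/30) = 0.141. For a common drift of 0.3 SD the noncentrality is 0.3/0.141 = 2.12 on 29 df.

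| Common drift | Active pre-post test significant | Range over splits |
|---|---|---|
| 0.2 SD | 28% | 19–39% |
| 0.3 SD | 54% | 35–71% |
| 0.4 SD | 78% | 56–92% |

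The adjusted active-vs-sham contrast stays at 5%.

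**Session order.** With imbalance, the order term multiplies the standard error by 1/√(1 − m²), where m is the difference in order counts divided by 30. At 20/10, m = 1/3 and the SE is 0.171 × 1.061 = 0.181. At 25/5, m = 2/3 and it is 0.171 × 1.342 = 0.229. Omitting the term can bias the result: with no TMS effect, second-day values shifted by 0.3 SD and 25 of 30 given sham first, the adjusted contrast without it has bias 0.113 and 9.3% false positives. With it, the figures are 0.000 and 4.9%.

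**The case against.** Both t-tests are labelled exploratory, and the general active-vs-sham sentence names no test, so a paired main analysis is not ruled out. That is correct. But these are the only biomarker tests the SAP names, so the label leaves the main comparison without a method, and the one active-vs-sham test that is written down does not fit the design.

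Most of the gain comes from pairing, not from the pre-TMS value. This also stands: 47% to 75%, against 75% to 81%. A paired post-TMS contrast would be defensible; adjustment is an improvement that depends on the biomarker. Using the pre-TMS value through simple change scores would be worse here: power at 0.5 SD is 68%, below the paired post-TMS test.

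The false-positive risk is conditional. It needs drift of a size the documents do not give, and a reader who ignores the sham result. The SAP never says a pre-post test alone establishes an effect. The independent test itself costs power and, with positive correlation, does not create false positives.

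Complete data are assumed. The MRI procedures section says each person does only some of the imaging tasks and allows people with incomplete assessments to stay in. With 24 or 20 complete pairs, adjusted power at 0.5 SD falls from 81% to 70% or 62%. The absolute figures are therefore optimistic, but the advantage of pairing remains.

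**Conclusion.** The concern holds. The named active-vs-sham test is wrong for the design described, and no other part of the document supplies a paired or baseline-adjusted contrast. Under the illustrative split, the independent test has 47% power at 0.5 SD, against 75% paired and 81% paired and adjusted. Paired analysis was better in all eight splits, each of which has positive between-session correlation. The pre-post test read alone would be significant in roughly 28% to 78% of trials under drift of 0.2 to 0.4 SD with no TMS effect.

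All variances, effect sizes and drifts are assumptions. The mismatch between design and test does not depend on them; the size of the loss does. This should be corrected. Confidence in the size is moderate.

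**What to change.** In the Statistical Analysis Plan:

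- Make the test of TMS effect for each biomarker the within-participant active-minus-sham difference in post-TMS values, adjusted for the active-minus-sham pre-TMS difference and session order. Use ANCOVA on within-person differences, or a mixed model with a participant random effect, condition, period and the session's pre-TMS value. Choose one. The ANCOVA drops incomplete pairs, so say how these are handled.
- Define baseline as that session's pre-TMS value.
- Replace the independent-sample t-test, and report pre-post tests as descriptive only.
- Do not let covariates enter this contrast because they tested significant.
- Report the order each participant received. If all had the same order, an order term cannot be fitted, and this must be stated as a limit. An order term does not deal with carryover between sessions.

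The cost is SAP wording and one or two degrees of freedom. No new measurements are needed, since all four values are already planned. The order term is almost free if orders are balanced (SE 0.171 against 0.170) and dearer if not (0.181 at 20/10, 0.229 at 25/5).
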